#### **6.1.4 Follow-up period**

Following the last dose of IMP (either as scheduled or prematurely), a post treatment follow-up should be scheduled for all patients 4 weeks ( $\pm 3$  days) after permanent IMP discontinuation.

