#### **10.4.1.4 Events of Special Interest**

An EOSI is a serious or non-serious AE of scientific and medical concern specific to the Sponsor's product or program, for which ongoing monitoring may be appropriate. Such events may require further investigation in order to characterize and understand them. These events should be reported on the specific e-CRF page (where applicable) and will only qualify for expedited reporting when serious (fulfilling SAE criteria).

The EOSIs for this study are:

- Major adverse cardiovascular events (MACE [cardiovascular death, myocardial infarction, or stroke]) and other specific CV events (eg, heart failure leading to hospitalization)
- Severe hypoglycemia (see [Section 10.6.1](#))
- Genital mycotic infections (to include vulvovaginal candidiasis in females and candidal balanitis in males)
- Urinary tract infections
- Clinically relevant volume depletion and events related/possibly related to volume depletion
- Diarrhea
- Pancreatitis
- Bone fractures
- Venous thrombotic events, to include deep venous thrombosis and thromboembolism (to include pulmonary embolism)
- Diabetic ketoacidosis
- Renal events, to include 50% decline in eGFR, end stage kidney disease, renal death
- Malignancies of special interest (breast, bladder, renal cell, Leydig cell, pancreatic, prostate, and thyroid cancer)
- Adverse event leading to an amputation

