1.6 STATISTICAL MODIFICATIONS MADE IN THE STATISTICAL ANALYSIS PLAN (SAP)

The statistical analysis plan history table below gives the timing, rationale, and key details for major changes to the statistical analysis features in the statistical analysis plan. Changes also incorporated in a protocol amendment are cross-referenced to [Table 1](#).

Statistical Analysis Plan

Version: 3

Lexicon Pharmaceuticals Protocol No. EFC14833

Date of Issue: 21-Nov-2019

Covance Study ID: 000000150524

Table 2 - Statistical analysis plan statistical changes

SAP version number	Date approved	Rationale	Description of statistical changes
1	30-May-2018		
1	30-May-2018		
1	30-May-2018		
1	30-May-2018	Randomization suspended under the original protocol	76 patients randomized under the original protocol
1	30-May-2018	As a result of the Amendment 1	Sensitivity analyses comparing sotagliflozin 400 mg versus placebo under Amendment 1 performed and presented for primary and secondary efficacy endpoints
1	30-May-2018	Urgent coronary revascularization not adjudicated by CEC to be consistent with CV outcome trials	Urgent coronary revascularization not included in adjudication related analyses **
1	30-May-2018	5 half-lives of sotagliflozin prolonged to 10 days considering patients with moderate renal dysfunction	5 half-lives of IMP updated from 5 days to 10 days; TEAE period updated accordingly **
1	30-May-2018	Baseline eGFR defined as recommended by CDISC Therapeutic Area Data Standards User Guide for Diabetic Kidney Disease	For serum creatinine and eGFR, the baseline value is defined as the average of all values before the first dose of double-blind IMP for those randomized and exposed or before randomization for those who were randomized but never exposed to IMP. **

Statistical Analysis Plan

Version: 3

Lexicon Pharmaceuticals Protocol No. EFC14833

Date of Issue: 21-Nov-2019

Covance Study ID: 000000150524

SAP version number	Date approved	Rationale	Description of statistical changes
1	30-May-2018	The effect in body weight considered more closely associated with the planned indication.	The order of secondary objectives / endpoints / multiplicity adjustment updated **
1	30-May-2018	Clarification on EOSI renal events	Details specified on renal events to be consistent with outcome studies in Section 2.1.4.2.
1	30-May-2018	[REDACTED]	[REDACTED]
1	30-May-2018	[REDACTED]	[REDACTED]
2	07-Jun-2019	[REDACTED]	[REDACTED]

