Sustained ≥50% decrease in eGFR	
(1) For ≥50% decrease in eGFR from baseline,
 
(1a) confirmed ≥50% decrease in GFR for ≥30 days with no reversible cause as recorded in eCRF "eGFR decrease", OR
 
(1b) positively adjudicated by CEC: Yes to the question "Does the subject meet the criteria of CKD progression" for ≥50% decrease in eGFR.

Sustained eGFR <15 mL/min/1.73 m ²	
(2) For eGFR <15 mL/min/1.73 m²,
 
(2a) confirmed eGFR <15 mL/min/1.73 m² for ≥30 days with no reversible cause as recorded in eCRF "eGFR decrease", OR
 
(2b) positively adjudicated by CEC: Yes to the question "Does the subject meet the criteria of CKD progression".

Chronic dialysis	
(3) For dialysis,
 
(3a) dialysis lasted for ≥90 days (e.g. end date – start date+ 1 ≥90) as recorded in eCRF "Renal Event – Dialysis", OR

Statistical Analysis Plan

Version: 3

Lexicon Pharmaceuticals Protocol No. EFC14833

Date of Issue: 21-Nov-2019

Covance Study ID: 000000150524

AE Grouping	Criteria
	(3b) positively adjudicated by CEC: Yes to the question “. Does the subject meet the criteria for ESRD”.
Renal transplant *	(4) “Renal transplant” captured in eCRF “Other procedure form”, where adjudication is not required. PTs of Renal transplant (10038533), Renal and pancreas transplant (10052278), Renal and liver transplant (10052279) based on MedDRA v22.0.
Renal death	(5) Renal death as positively adjudicated by CEC: “Death - Non-Cardiovascular (Renal)” as the primary cause of death
EOSI not adjudicated *	
Severe hypoglycemia	algorithm specified in Section 2.1.4.1 based on eCRF “Hypoglycemic Events”
Genital mycotic infections	PTs in Appendix C
Urinary tract infections	PTs in Appendix C
Clinically relevant volume depletion and events related/possibly related to volume depletion	PTs in Appendix C
Diarrhea	Narrow search on “Noninfectious diarrhoea (SMQ)” [20000218] plus the following PTs (MedDRA v22.0): Gastroenteritis (10017888), Antidiarrhoeal supportive care (10055660), Enteritis (10014866), Enteritis leukopenic (10014877), Enterocolitis (10014893), Enterocolitis haemorrhagic (10014896)
Pancreatitis	PTs in Appendix C
Venous thrombotic events	PTs in Appendix C

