For the EOSI renal events where selected events are adjudicated, the number (%) of patients with any renal events identified in [Table 3](#) in [Section 2.1.4.2](#) will be summarized by treatment group.

Statistical Analysis Plan

Version: 3

Lexicon Pharmaceuticals Protocol No. EFC14833

Date of Issue: 21-Nov-2019

Covance Study ID: 000000150524

The following renal events will be listed along with the adjudication outcome if applicable, including events,

- i. recorded in eCRF “GFR decrease”,
- ii. recorded in eCRF “Renal Event – Dialysis”,
- iii. identified as “Renal transplant” in eCRF “Other procedure”,

Renal death will be part of all deaths specified above.

Other EOSIs

For EOSIs that are not adjudicated, the number (%) of patients with at least one event will be summarized by treatment group and by PT (as identified in [Table 3](#) in [Section 2.1.4.2](#)).

Severe hypoglycemia will be included in the summary of hypoglycemia (See [Section 2.4.5.1](#)).

AE leading to an amputation is described in the section below.

Analysis of Amputation

The number (%) of patients with amputation will be summarized by treatment group and by PT and LLT during the study (ie, regardless of on- or post-treatment). Amputation is a procedure recorded in eCRF “Other Procedures related to Amputation”. Patients who had a procedure related to amputation will be listed.

The number (%) of patients with an “AE leading to an amputation” will be summarized by treatment group and by PT. The “AE leading to an amputation” is determined by the AE identifier recorded in eCRF “Other Procedures related to Amputation” when “AE correction” is chosen as the reason for the amputation procedure.

In addition, the number (%) of patients with an “AE potentially leading to an amputation” will be summarized by treatment group and by PT (as identified in [Table 3](#) in [Section 2.1.4.2](#)). These PTs in [Table 3](#) were requested by the European Medicines Agency (EMA)/ Pharmacovigilance Risk Assessment Committee (PRAC) Assessment Report, 9 February 2017). The associated list will be provided as well, with patients who had an amputation procedure flagged. “AE potentially leading to an amputation” represents the condition that may potentially lead to the amputation procedure, but not in all cases an amputation has occurred.

Analysis of pretreatment and posttreatment adverse events

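### SAP Table 3 narrows the listed renal event from a 50% eGFR decline to a sustained or CEC-positive one, and planned visits usually cannot show 30 days for a decline first seen at Week 26

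*SAP*

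**What the plan says.** Protocol 10.4.1.4 defines the event category as "Renal events, to include 50% decline in eGFR, end stage kidney disease, renal death". SAP 2.1.4.2 repeats that wording in its own list of events of special interest. Neither place attaches a minimum duration or a condition on cause.

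Table 3 in the same SAP section then labels the row as a sustained decrease and gives two routes joined by OR:

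- Route 1a: a "confirmed ≥50% decrease in GFR for ≥30 days with no reversible cause as recorded in eCRF" form for eGFR decreases.
- Route 1b: "positively adjudicated by CEC: Yes to the question" whether the subject meets the criteria of CKD progression, for a decrease of at least 50%.

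SAP 2.4.5.2 tabulates "the number (%) of patients with any renal events identified in" Table 3, by treatment group. It also lists the events recorded on the eCRF form for GFR decreases, with the adjudication outcome where there is one. The SAP change log (SAP 1.6, version 1) gives the reason: "Details specified on renal events to be consistent with outcome studies in Section 2.1.4.2".

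On timing, Protocol 6.1.4 says that "a post treatment follow-up should be scheduled for all patients 4 weeks" (±3 days) after permanent discontinuation. In the flow chart (Protocol 1.2), chemistry is drawn after baseline at Weeks 4, 8, 12, 18, 26 and 30.

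**The concern.** The count in the renal table is narrower than the event that the protocol and the SAP's own list name. A patient whose eGFR halves and then recovers, or whose decline has an identified reversible cause, meets the listed event. That patient does not enter the count unless the CEC answers yes on CKD progression. Protocol 4.4 names both severe renal events and volume depletion among the risks to be watched closely, so a reversible fall in eGFR is not a side issue for this drug.

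The 30-day rule was also brought in for consistency with outcome studies. In a trial with 26 weeks of treatment and one visit four weeks later, it does not fit the end of the schedule. What is at stake is whether the renal table shows the number of patients per arm with the event the protocol lists.

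**Working it through.** **Inputs.** Nominal chemistry days from Protocol 1.2: 28, 56, 84, 126, 182 and 210 (Weeks 4, 8, 12, 18, 26 and 30), each ±3 days. The follow-up visit is 28 ±3 days after last dose (Protocol 6.1.4). The confirmation rule is at least 30 days (SAP Table 3). The MDRD exponent on creatinine is -1.154 (SAP 2.5.1). Creatinine and eGFR abnormality (PCSA) criteria are from SAP Appendix B.

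**The plan's own interval.** 210 - 182 = 28 days, which reproduces the stated 4 weeks.

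**Can a later planned visit show 30 days?**

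| First seen | First later planned visit at least 30 days away | Gap (days) |
|---|---|---|
| Week 4 | Week 12 | 84 - 28 = 56 |
| Week 8 | Week 18 | 126 - 56 = 70 |
| Week 12 | Week 18 | 126 - 84 = 42 |
| Week 18 | Week 26 | 182 - 126 = 56 |
| Week 26 | none | only 210 - 182 = 28 |
| Week 30 | none | 0 |

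On nominal days, the last first-detection day that a planned visit can confirm is 210 - 30 = Day 180.

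**Effect of the windows on Week 26.** Counting from last dose, Visit 10 falls at 25 to 31 days, so 30 is reached only at +2 or +3 days (from +1 if days are counted inclusively). Letting both visits float, the gap runs from 207 - 185 = 22 to 213 - 179 = 34 days. Of the 7 × 7 = 49 day combinations, 15 reach 30 elapsed days. That is a count of combinations, not a probability.

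**What the other tables show.** With age taken as fixed, eGFR is proportional to creatinine^(-1.154).

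- A 50% fall needs a creatinine ratio of 2^(1/1.154) = 1.82, a rise of about 82%.
- A doubling of creatinine gives 2^(-1.154) = 0.449, a fall of about 55%.
- A 30% creatinine rise gives 1.3^(-1.154) = 0.739, a fall of about 26%.

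The creatinine criteria sit at 30% and 100%. The 30% row therefore contains every halving in the period but mixes it with falls from about 26% upward. The 100% row misses halvings with a creatinine rise between about 82% and 100%. The eGFR criteria are absolute bands, not percentage changes. PCSA summaries cover the TEAE period, which ends 10 days after last dose (SAP 2.1.4), so an on-time Week 30 value at 28 days is outside them.

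**The case against.** Much can be said for the plan, and most of it stands.

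- A reader might infer that a halving counts only if it lasts 30 days. The documents do not say that. Route 1b is an alternative, and the SAP writes no duration or reversibility condition into it. Whether the committee's criteria for CKD progression require persistence is in a charter that is not supplied, so it cannot be claimed that route 1b fails to pick up acute events.
- A reader might infer that late declines are lost. SAP 2.1.4 follows these events to the last planned visit or to resolution or stabilization, whichever is later. Protocol 10.4.2 allows observation beyond the last visit, and Protocol 9.2.1.3 accepts central retests. Route 1a relies on what the eCRF records, not on scheduled visits. What remains is that no planned visit reliably supplies the 30-day value.
- The 28-day gaps after Weeks 4 and 8 are not a comparable problem, because a decline that persists is confirmed at the later visits shown above.
- Events on the eCRF form are listed without a 30-day condition, and patients with a creatinine abnormality have their full profile listed. These are real safeguards, but neither gives a count of halvings by arm.
- The rule that "dialysis lasted for ≥90 days" may look like the same fault. It is not: the protocol names end stage kidney disease, for which a chronicity rule is a fair reading. It works from eCRF dates and has its own CEC route.
- The narrowing is labelled as sustained and disclosed in the change log, and the safety analyses are descriptive. Both are true. Neither reconciles Table 3 with the unqualified event named in the list earlier in the same section.

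**Conclusion.** The point holds as a mismatch of definition with a limited timing consequence. The listed event is a 50% decline; the counted event is a sustained decline without reversible cause, or a CEC-positive one. Short or reversible halvings that are not CEC-positive are left out of the count, although they may appear in listings and in the creatinine rows. For a halving first seen at Week 26, the on-time Visit 10 is 28 days away, which is 2 days short. For one first seen at Week 30 there is no later planned visit.

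This rests on the flow-chart chemistry days and on a CEC charter that was not available. The documents give no rate for this event, so the number of patients affected cannot be estimated; it is expected to be small. A reader might go further and infer that the renal table will hide a renal signal. It could show fewer events than the central-laboratory data contain, but nothing in the documents shows that it will, or that one arm would be affected more than another. This is a cheap improvement to safety reporting, not a threat to the trial's conclusions.

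**What to change.** In SAP Table 3 and SAP 2.4.5.2:

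1. Add a row by treatment group for any post-baseline central-laboratory eGFR at least 50% below baseline, whatever its duration or cause, using the SAP's existing eGFR baseline (the average of pre-dose values).
2. Keep the sponsor's sustained definition and the CEC-adjudicated events as sub-rows beneath it.
3. State that a halving seen at Week 26 and still present at the Week 30 visit counts as confirmed by visit. A fixed day count is less safe: 28 - 3 = 25 days would not cover the 22-day lower end of the window range.
4. Show halvings still unconfirmed at last contact as unconfirmed.

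The cost is some SAP wording and one derived row from data already collected, with no added visit or sample. The table may show a few more events, mostly transient, and the sub-rows let a reader see which are sustained.

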2.1.4.3 Deaths

The deaths observation period are per the observation periods defined above.

- Death on-study: deaths occurring during the on-study observation period
- Death on-treatment: deaths occurring during the TEAE period
- Death post-study: deaths occurring after the end of the study

2.1.4.4 Laboratory safety variables

Clinical laboratory data consists of blood analysis (including hematology, clinical chemistry, amylase, lipase and lipid profile) and urinalysis. Clinical laboratory values will be summarized in both standard international units and conventional units when applicable.

Blood samples for clinical laboratories will be collected at designated visits (see study flowchart in [Appendix E](#)). The following laboratory data will be measured at a central laboratory:

- Hematology
 - **Red blood cells and platelets:** hemoglobin, hematocrit, red blood cell, platelets count
 - **White blood cells:** white blood cell, neutrophils, lymphocytes, monocytes, basophils, eosinophils
- Clinical chemistry
 - **Metabolism:** glucose (serum), creatine phosphokinase (CPK),
 - **Electrolytes and minerals:** sodium, potassium, chloride, bicarbonate (ie, carbon dioxide), calcium, phosphorus, magnesium
 - **Renal function:** blood urea nitrogen (BUN), creatinine, uric acid,
 - **Liver function:** total protein, albumin, ALT, aspartate aminotransferase (AST), alkaline phosphatase (ALP), total bilirubin, Lactic acid dehydrogenase (LDH)
- Lipid parameters (fasting): total cholesterol (TC), high density lipoprotein cholesterol (HDL-C), low density lipoprotein cholesterol (LDL-C) (calculated by Friedwald equation, See [Section 2.5.1](#)), Non-HDL-C (calculated as the difference between TC and HDL-C), triglycerides (TG).

Statistical Analysis Plan

Version: 3

Lexicon Pharmaceuticals Protocol No. EFC14833

Date of Issue: 21-Nov-2019

Covance Study ID: 000000150524

- Pancreatic enzymes: lipase, amylase.
- Markers of Intestinal Transit and Absorption: Vitamins: B6, B12, K, E and A, Serum folate, and Ferritin
- Markers of bone and calcium metabolism
 - Calcium,
 - 25-hydroxyvitamin D,
 - 1,25-dihydroxyvitamin D,
 - Phosphorus,
 - Parathyroid hormone (PTH),
 - Markers of bone resorption: N-terminal telopeptide (NTX), beta-C-terminal telopeptide (β -CTX-1),
 - Marker of bone formation: type 1 procollagen N-terminal (P1NP)

Urine samples will be collected at designated visits (see study flowchart in [Appendix E](#)). The following laboratory data will be measured at a central laboratory:

- Urine dipstick includes: specific gravity, pH, protein, blood, ketones, bilirubin, urobilinogen, nitrite, and leukocyte esterase
- Urine microscopy includes, but is not limited to: detection of formed cellular elements, casts, bacteria, yeast, parasites, and crystals in centrifuged urine sediment
- Urine markers of bone and calcium metabolism: calcium and phosphorus.
- Urine albumin, calcium, glucose and creatinine

Serum glucose, UGE, calculated urine ACR and calculated urine GCR will be presented as efficacy parameters in [Section 2.4.4](#). For creatinine and calculated eGFR, PCSA summaries will be presented in the safety section while descriptive summaries in the efficacy section.

Technical formulas are described in [Section 2.5.1](#).

2.1.4.5 Vital signs variables

Vital signs include: heart rate (HR), systolic and diastolic blood pressure, temperature, and respiratory rate (see study flowchart in [Appendix E](#) for designated visits). They will be performed after the patient has been seated for at least 5 minutes. Blood pressure and HR will be assessed 3 times with at least 1 minute between each measurement following the 5-minute rest period. The mean of the 3 measurements will be analyzed for each vital sign variable (HR, SBP, and DBP).

2.1.4.6 Physical examination

A complete physical exam will be performed at Visit 1 (Screening) and Visit 9 (Week 26). “Normal”, “Abnormal” or “Not done” as determined by the Investigator will be reported in the e-CRF by body system.

Statistical Analysis Plan

Version: 3

Lexicon Pharmaceuticals Protocol No. EFC14833

Date of Issue: 21-Nov-2019

Covance Study ID: 000000150524

2.1.4.7 *Electrocardiogram variables*

12-lead ECGs will be performed at Visit 1 (Screening), Visit 3 (Randomization) and Visit 9 (Week 26). ECG status of “normal” or “abnormal” will be reported in the e-CRF as determined by the investigator.

2.1.5 *Pharmacokinetic variables*

Pharmacokinetic variables include the concentration of sotagliflozin and its 3-O-glucuronide metabolite in the sotagliflozin group.

2.2 DISPOSITION OF PATIENTS

This section describes patient disposition for both patient study status and the patient analysis populations.

Screened patients are defined as all patients who have signed the informed consent.

Randomized patients consist of all patients with a signed informed consent form who have had a treatment kit number allocated and recorded in the IRT database, regardless of whether the treatment kit was used or not.

For patient study status, the total number of patients in each of the following categories will be presented in the clinical study report using a flowchart diagram or summary tables:

- Screened patients
- Run in patients: patients who had a run-in record in IRT,
- Screen failure patients (including failures during run-in) and reasons for screen failure (see [Appendix A](#) for details on the mapping of inclusion and exclusion criteria under the original protocol and Amendments)
- Nonrandomized but treated patients
- Randomized patients
- Randomized but not treated patients
- Randomized and treated patients
- Patients who have completed the 26-week double-blind treatment period as scheduled
- Patients who did not complete the 26-week double-blind treatment period as scheduled and the reasons for permanent treatment discontinuation
- Patients who have completed the study as scheduled
- Patients who did not complete the study as scheduled and the reasons for study discontinuation

Statistical Analysis Plan

Version: 3

Lexicon Pharmaceuticals Protocol No. EFC14833

Date of Issue: 21-Nov-2019

Covance Study ID: 000000150524

- Patients' end of study status (completed, not completed) and corresponding end of treatment status (completed, not completed)
- Status at last study contact.

For screened, run in, screen failure, and nonrandomized but treated patients, percentages will be calculated using the number of screened patients as the denominator. All other categories of patients will be presented by treatment group and the percentages will be calculated using the number of randomized patients within each treatment group as the denominator. Reasons for treatment discontinuation will be supplied in tables giving numbers and percentages by treatment group. Patients prematurely discontinued from treatment and/or study, along with reasons for discontinuation, will also be listed.

A summary of the distribution of patients by country and center will also be provided (overall number of patients screened, run-in, randomized, and treated, as well as number of patients randomized, discontinued from study treatment, and discontinued from study for each treatment group).

Patients treated but not randomized, patients randomized but not treated and patients randomized but not treated as randomized will be identified and described in separate listings. The patients of the third category (randomized and not treated as randomized) will be part of efficacy and safety analyses (see [Section 2.3](#)). Patients randomized but not treated will be included in efficacy analysis. Safety data of patients treated but not randomized will be reported separately.

The randomization strata [HbA1c at Screening ($\leq 8.0\%$, $>8.0\%$) and mean SBP (<130 , ≥ 130 mmHg)] assigned by IRT will be summarized. The percentages will be calculated using the number of randomized patients as the denominator. The discrepancy between the strata assigned by IRT and the information reported on e-CRF will be listed for all randomized patients.

Kaplan-Meier (KM) plots of the cumulative incidence of double-blind IMP discontinuations due to any reason and due to AEs will be provided for the double-blind treatment period separately (see [Section 2.5.4](#)). A listing of these patients, along with the reason for discontinuation of treatment, study completion status and the reason for discontinuation study, will be provided.

All important deviations including randomization and drug-dispensing irregularities will be summarized in tables giving numbers and percentages of deviations by randomized treatment group.

Additionally, the analysis populations for safety, efficacy, and pharmacokinetics defined in [Section 2.3](#) will be summarized in a table by number of patients in the randomized population.

- Efficacy population: intent-to-treat (ITT) population
- Safety population
- PK population.

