### **10.3.4 Handling of patients after permanent treatment discontinuation**

Every effort should be made to maintain patients in the study. Patients should be followed up according to the study procedures as specified in this protocol up to the scheduled date of study completion, or up to recovery or stabilization of any AE to be followed-up as specified in this protocol, whichever comes last.

If a patient prematurely discontinues study treatment, a Premature EOT visit (see [Section 10.1.2.1.2](#)) should be scheduled prior to treatment discontinuation, if possible. If not possible, the Premature EOT should be scheduled as soon as possible after treatment discontinuation. In the case of early discontinuation, no sample for measuring plasma concentration should be taken at the Premature EOT visit, nor at any subsequent visits. For patients who discontinue treatment but remain in the study, the remaining visits should occur as scheduled where possible. The IRT should be notified of EOT.

After premature permanent discontinuation of the IMPs, any treatments (other than SGLT2 inhibitors) are permitted, as deemed necessary by the Investigator.

All cases of permanent treatment discontinuation should be recorded by the Investigator in the appropriate pages of the e-CRF when considered as confirmed.

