2.1.3 Efficacy endpoints

All efficacy measurements collected during the study will be considered for analyses, including those obtained after IMP discontinuation or introduction of rescue therapy (see [Section 2.5.4](#)).

HbA1c, 2-hour PPG, FPG, urine ACR, UGE, urine GCR, serum creatinine, and eGFR are measured/calculated in a central laboratory (see study flowchart in [\).](#) Body weight, SBP and DBP (see [Section 2.1.4.5](#)) are measured at on-site visits by the investigator. Patients requiring rescue are identified as those with the reason for treatment ticked “rescue therapy” in e-CRF “Medication” page.

Efficacy variables will be summarized in both standard international units and conventional units when applicable.

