2.4.4.3 Analyses of other efficacy endpoints

The analysis of other endpoints (see [Section 2.1.3](#)) will be descriptive with no formal testing. Summary statistics at scheduled visits based on observed value will be provided by each treatment group. Graphical presentations will also be used to illustrate trends over time as appropriate.

The number (%) of patients who used rescue therapy and a KM curve for the time to first rescue therapy will be provided by treatment group. A list of patients who used rescue therapy will also be provided (see [Section 2.5.4](#)).

Urine ACR will be log-transformed at patient level. Summary statistics of urine ACR in log scale will then be calculated for each treatment group at each visit and back-transformed to provide the geometric mean and its associated percent change of urine ACR from baseline.

Shift tables will be provided for urine ACR at Week 26 using the pre-defined categories. That is, the number (%) of patients with progression from one category at baseline to another category at Week 26 will be provided by treatment group. The pre-defined categories are, for urine ACR, < 30 mg/g creatinine [Normal], ≥ 30 to < 300 mg/g creatinine [Microalbuminuria], and ≥ 300 mg/g creatinine [Macroalbuminuria].

The analysis of the 2-hour PPG endpoint will be based on a Time 0 adjusted value (ie, the 2-hour PPG value minus the Time 0 value, FPG sample) at both the Baseline and Week 26 time points. These Time 0 adjusted values will be used to derive the Week 26 minus Baseline scores, which will serve as the measure of interest for comparative purposes.

Statistical Analysis Plan

Version: 3

Lexicon Pharmaceuticals Protocol No. EFC14833

Date of Issue: 21-Nov-2019

Covance Study ID: 000000150524

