As specified in the study protocol, laboratory data from scheduled visits are reported by central laboratories. The local results will not be used in the efficacy analyses or in the definition of baseline for both safety and efficacy analyses. In the safety analyses, for parameters with PCSA defined based on normal range, local results will only be used in the PCSA summary if they are accompanied by a local laboratory normal range. For parameters with PCSA not defined based on normal range, local results will be used in the PCSA summary as appropriate.

When a patient has more than 1 measurement from the central laboratory for the same laboratory parameter on the same date, the average of the measurements will be used. For the same laboratory parameter, if a patient has more than 1 measurement on different dates for the same scheduled visit, the value closest to the date of the visit will be used for the scheduled visit. When the values for the same scheduled visit are equidistant, the last value should be used for the scheduled visit. Similar rules will be applicable to a patient who has more than 1 set of measurements for the same vital sign parameter (ie, SBP, DBP, or HR) on the same date.

Time to event analysis

For time to event analysis/KM plot, time to event (eg, treatment discontinuation, rescue therapy, hypoglycemia, etc) is defined as the number of days from the date of the first administration of double-blind IMP (or the date of randomization if not exposed) to the start date of the first occurrence of the event during the 26-week double-blind treatment period.

Patients who did not experience any event during the 26-week double-blind treatment period are considered censored observations. For time to treatment discontinuation/rescue therapy, censoring date is the date of EOT. For time to severe or documented hypoglycemia, censoring date is date of EOT+1 or date of EOS, whichever is the earliest. Date of EOS will be used if date of EOT is not available. Last contact date will be used if date of EOS is not available.

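### The Kaplan-Meier plot of IMP discontinuation due to AEs is labelled cumulative incidence but censors other-cause stops, so it overstates AE discontinuation

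*SAP*

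**What the plan says.** SAP 2.2 (Disposition of patients) promises "Kaplan-Meier (KM) plots of the cumulative incidence of double-blind IMP discontinuations due to any reason and due to AEs" over the double-blind period and refers to SAP 2.5.4 for the details. The time-to-event rules in SAP 2.5.4 state: "Patients who did not experience any event during the 26-week double-blind treatment period are considered censored observations". They go on: "For time to treatment discontinuation/rescue therapy, censoring date is the date of EOT". Neither document names a competing-risk method or has a separate rule for patients who stop IMP for a reason other than the one being plotted.

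SAP 2.2 also gives crude figures next to the plots: "Reasons for treatment discontinuation will be supplied in tables giving numbers and percentages by treatment group". Randomized patients in each arm are the denominator.

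**The concern.** Protocol 10.3.2 defines permanent discontinuation as a definitive decision that the patient will not take IMP again. Someone who stops because of withdrawal, poor compliance or any other non-AE reason can therefore never become an AE discontinuation. Censoring treats that patient as still able to have the event later, at the same rate as those who remain on IMP.

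The resulting curve estimates the AE-stop risk in a hypothetical setting without other-cause stops. The label promises something else: the proportion of patients who actually stopped because of an AE. The gap grows with the number of other-cause stops, so two arms with the same true AE-stop incidence can show different curves. A reader who compares tolerability by eye would see part of that difference as a drug effect. The curve would also disagree with the percentage by reason in the disposition table.

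**Working it through.** **Inputs from the documents.** Estimator and label: SAP 2.2. Censoring rule: SAP 2.5.4. EOT is read as the end of IMP treatment, which fits the EOT+1 rule for hypoglycemia in the same section. The documents give no discontinuation rates by cause and no figure for these curves, so there is no stated number to reproduce.

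**Assumed inputs.** Proportion stopping for an AE by Week 26, *a*: 5% or 10%. Proportion stopping for another reason, *o*: 0 to 20%. Cause-specific hazards are constant over the 26 weeks.

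**Formulas.**
- Total cumulative hazard: H = −ln(1 − a − o)
- AE share of it: H_AE = H × a/(a + o)
- End of the planned curve: 1 − KM = 1 − exp(−H_AE)
- Correct value (Aalen-Johansen): a

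**Worked example, a = 5%, o = 15%.** H = −ln(0.80) = 0.2231. H_AE = 0.2231 × 0.05/0.20 = 0.0558. 1 − exp(−0.0558) = 5.43%. The excess is 0.43 points, or less than one patient per 100.

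**Grid of 1 − KM at Week 26.**

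| True AE stops | Other 0% | Other 5% | Other 10% | Other 15% | Other 20% |
|---|---|---|---|---|---|
| 5% | 5.00% | 5.13% | 5.27% | 5.43% | 5.59% |
| 10% | 10.00% | 10.27% | 10.56% | 10.87% | 11.21% |

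With any other-cause stops, the excess runs from 0.13 points (5.13 − 5.00) to 1.21 points (11.21 − 10.00).

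**Artificial difference between arms with equal true AE stops.**
- AE 5% in both arms, other-cause 5% versus 15%: 5.43 − 5.13 = 0.3 points.
- AE 10% in both arms, other-cause 5% versus 20%: 11.21 − 10.27 = 0.9 points.

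**Dependence on timing.** If all other-cause stops came after the last AE stop, there would be no excess. If all came before the first AE stop, the curve would end at a/(1 − o): 5/85 = 5.9% for a = 5%, o = 15%, and 10/80 = 12.5% for a = 10%, o = 20%. The constant-hazard figures lie between these limits.

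**Any-reason curve.** Every IMP stop is an event, so no competing stop is left to censor, and o = 0 in the formula. This bias does not arise.

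**The case against.** The strongest objection is that little depends on the plot. No endpoint, test or step in the multiplicity sequence uses it. The plan already gives the number and percentage of stops by reason over randomized patients, TEAEs leading to discontinuation (SAP 2.4.5.2), and a listing of patients with reasons. Where treatment status is complete, the crude percentage by reason is the Week 26 AE-stop incidence without this bias. In the worked example the error is under half a point. All of this stands, and it limits the importance of the point. It does not make the label correct, and it means the report would show two different figures for the same quantity.

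A reader might extend the argument to rescue, because SAP 2.4.4.3 says "a KM curve for the time to first rescue therapy will be provided by treatment group" and the same EOT censoring applies, and conclude that the rescue curve is also biased upward. The documents do not support that:
- SAP 2.4.4.3 does not call the rescue curve a cumulative incidence.
- IMP stop does not rule out later rescue. Protocol 10.3.4 says "For patients who discontinue treatment but remain in the study, the remaining visits should occur as scheduled where possible", and that after IMP stop "any treatments (other than SGLT2 inhibitors) are permitted, as deemed necessary by the Investigator".
- SAP 2.1.3 identifies rescue from an e-CRF entry ("Patients requiring rescue are identified as those with the reason for treatment ticked" as rescue therapy), with no stated restriction to time on IMP.

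The direction of any bias therefore depends on a target that the SAP does not state. In a simulation with assumed constant hazards, 1 − KM for rescue of 10% and 20% IMP stops, rescue by Week 26 regardless of IMP was 9.5%, 10.0%, 11.0% or 12.7% when the hazard after IMP stop was 0.5, 1, 2 or 4 times the on-IMP hazard. Kaplan-Meier could overstate, match or understate it.

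**Conclusion.** The point holds for the AE-specific discontinuation plot only. Read literally, SAP 2.2 and 2.5.4 together produce a curve that overstates the incidence of AE discontinuation in every arm where other-cause stops precede AE stops, and by more in an arm with more of them. For assumed AE stops of 5 to 10% and other-cause stops of 5 to 20%, the excess is about 0.1 to 1.2 points under constant hazards. The artificial between-arm difference is 0.3 to 0.9 points in the two scenarios shown. All the rates are assumptions, and the size also depends on when the stops occur.

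The importance is low: the plot is descriptive, and primary and secondary inference is untouched. No conclusion about the direction of bias in the rescue curve follows.

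**What to change.** In SAP 2.2, split the sentence on the discontinuation plots: Kaplan-Meier for discontinuation for any reason, and the Aalen-Johansen cumulative incidence by arm for discontinuation due to AEs. In SAP 2.5.4, add that for the AE-specific curve a permanent IMP stop for any other reason is a competing event and is not censored, while patients who complete treatment are censored at EOT as now.

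As a check, the Week 26 value of the AE curve should then agree with the crude percentage by reason wherever treatment status is complete.

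The cost is a sentence in each section and a change of estimator in one plotting program. The date and reason for each IMP stop are already collected, so no new data are needed.
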